Demographic data interview & record review (co-variables)	X		
Medical and surgical history (co-variables)	X		
Complications - emergency department visit, hospitalization (co-variables)			X

(g) General analytic plan (statistical analysis):

Primary Hypothesis.

In patients undergoing sedated colonoscopy for screening, when all polypoid and flat lesions including diminutive ones proximal to the splenic flexure are removed by polypectomy or biopsy, the patients examined by the combined chromoendoscopy and water method will be found to have a higher proportion of individuals with at least one proximal diminutive adenoma compared with the water method alone or air insufflation method for aiding insertion of the colonoscope.

Statistical Analysis: We will summarize the variables collected by calculating the frequencies of the categorical variables [such as number of patients with at least one proximal diminutive adenoma (proximal diminutive ADR), number of adenomas detected, adenoma location, adenoma size, gender, ethnicity, etc) and calculating the mean and standard deviation of the continuous variables (such as adenoma size, volume of water used, age, BMI, etc)].

To investigate differences in ADR, we will use logistic regression models, with an outcome that is a binary variable denoting whether each subject had one or more diminutive proximal adenomas. These models will allow us to quantify the differences between the three tests and determine if the differences are statistically significant. We will account for demographic characteristics (age, gender, BMI, ethnicity, etc) and investigate how other primary covariates (procedure time, volume of water used in study, etc) affect the rate of adenoma detection. Following, we will investigate the effects of secondary covariates (colon cancer detected, sedation medications) on adenoma detection rates.

As a secondary analysis, we will investigate how the secondary outcomes vary among the three tests. We will use repeated measures ANOVA and logistic regression models to quantify the differences between tests and to determine if they are statistically significant.

Pitfalls and solution

The report by Kahi et al. [20] did not demonstrate a significant difference in the adenoma detection between chromoendoscopy with HD scope and HD white light colonoscope alone. The failure to demonstrate a significant difference may be the result of a type II error. The authors did state that they would require upward of 800 patients in order to show a significant difference.

The time consuming procedure of dye spraying may also be a deterrent to the routine use of chromoendoscopy. However, our pilot data using combined chromoendoscopy and water method with high resolution colonoscopes did demonstrate a much higher ADR and with the additional benefits of the water method over the conventional air technique, it would be prudent to evaluate the potential impact of this combined method in enhancing adenoma detection in routine CRC screening.

The significance of small adenoma in the future development/advancement to CRC remains controversial and needs to be addressed. Most of the current publications referred to identification of relatively larger adenoma. In previous RCT, our experience suggested that small polyps and adenoma are better visualized using the water method with or without chromoendoscopy. Indeed, Kahi et al. [20] also reported a significantly higher detection of <5 mm adenomas and flat adenomas in the chromoendoscopy group suggesting that dye staining enhances the appearance of small lesions. Air distension tends to stretch the colonic mucosa making small lesions less obvious under white light examination. A combined chromoendoscopy and water method reveals the small lesions by outlining their contour and highlighting mucosal abnormalities (Figure 4). Improved visualization allows the biopsy or removal of these small lesions. The water method enhances the observation of small lesions especially those on the right side which are more likely to be missed due to poor preparation and failed cecal intubation.

A number of genetic and environmental factors influence the growth and progression of small adenoma [66]. One recent study reported that of the 3291 colonoscopies performed, 1235 colonoscopies yielded a total of 1933 small or diminutive adenomatous polyps. Advanced histology including carcinoma was found in 10.1%

5-10 mm adenomas and in 1.7% of ≤4 mm adenomas [67]. It is logical to expect that with the adenoma-cancer sequence concept, a proportion of small polyps can grow/evolve to become dysplastic and eventually cancer. Therefore even small lesions especially those on the right side should be biopsied or removed because of the potential risk of future malignancy [7,8]. Once detected on screening colonoscopy and confirmed pathologically, the finding (adenomas or flat lesions) would change the recommendation for subsequent surveillance. The lack of mortality reduction by optical colonoscopy for right-sided cancer has not been explained and this may be related to miss lesions. These considerations justify the detection and removal of diminutive lesions during optical colonoscopy, especially those in the right colon. However, only long term follow up studies will be able to show if removal of the right-sided small adenomas will prevent future development of colon cancer. We will continue to follow this cohort of patients when they return for surveillance colonoscopy or with symptoms of colorectal cancer.

The presence of poor bowel preparation could limit examination. The presence of stool could change the color of the indigo carmine solution turning it green instead of blue color. We emphasize the need for suction removal of the dirty water from the colonic lumen before infusion of clean (colored) water to clear the view for visualization and enhance the staining effects of indigo carmine. Dye staining serves to highlight the contour and contrast between the polyp and adjacent mucosa thus improving observation of the lesions.

Other issues

Issues related to expectation. Expectation of benefit (e.g. finding more lesions) cannot be avoided by the colonoscopist who is not blinded. We'll monitor changes in process variables (variables that reflect the presumed mechanism of treatment, e.g. cecal intubation documented by photograph of the appendix orifice and or cecal folds, withdrawal time, rate of adenoma detection (e.g. control group should meet the quality standard of having an ADR of 25% in male patients undergoing screening).

Issues related to blinding of endoscopist. The colonoscopist and nurse cannot be blinded to treatment allocation and the primary outcome of proximal diminutive ADR. Randomly selected (10% of total determined by the statistician) coded digital records will be reviewed by independent paid observers to confirm agreement of lesions, cecal intubation, times (endoscopic clock) of insertion, cecal intubation and total withdrawal of the colonoscope. For secondary outcomes, to compensate for increased risk of investigator bias, this study will be designed to use independent, blinded evaluators, whenever indicated, for assessment of outcome(s). No analysis will be started until all patients have completed evaluation to avoid biasing the colonoscopist, who may change the approach if it is known that one group is doing better or worse than the other.

Issues related to male dominance in enrollees. While patients of both sexes will be enrolled, it is likely that there will be a predominance of male enrollees. This is unavoidable because the VA population consists of 95% male and 5% female.

Issue related to differential dropout rate. Since sedation is provided for all groups of patients, we expect the patient tolerance will be similar. Any dropouts will be retained in the data analysis (intent-to-treat) and labeled treatment failures (no adenomas in the unexamined segment) to avoid any differential dropout rate to seriously bias outcomes.

Issues related to the water techniques used to insert the colonoscope lack standardization. The insertion technique for the water method will be standardized (56) by having the air pump turned off until the cecum is reached. Air pockets are suctioned on scope insertion. Dirty water is suctioned before clean water is infused to facilitate scope advancement and to minimize the volume of water inside the patient in case the patient becomes incontinent. Close attention will be paid to keep record of these variables to detect unavoidable variations.

(I) Publication from Last Funding Period (Pertinent Publications)

RESEARCH PAPERS - PEER REVIEWED

[name], Mann S, Leung FW. Option for screening colonoscopy without sedation – a pilot study in United States veterans. *Alimentary Pharmacology and Therapeutics* 2007; 26(4):627-631.

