4. Response: In addition to the Sacramento VA data, the Sepulveda VA data are presented in Tables 3 and 5. Data collected by our collaborator, [name] at the Phoenix VA, confirm the water method increases ADR (overall and in the proximal colon, particularly diminutive ones). The abstract will be presented at the DDW – ASGE Oral Session on Cutting Edge Colonoscopy Technology 2011. Thus, comparable observations demonstrating the water method to exert a positive impact on ADR have been forthcoming from three VA sites. To highlight the importance of the water method, this technique is being featured in two symposia in the upcoming DDW in May 2011 where the water method will be presented and discussed in special topic forum and symposium on cutting edge colonoscopy technology. Important publication including an *Endoscopy Innovation Forum* paper will be published. We have organized two Colorectal Cancer Screening Symposium at the Sacramento VAMC where the water method was presented and its application and benefits discussed.

5. Response: We have limited the number of secondary outcomes. They include overall adenoma detection rate, cecal intubation success rate and sedation medication requirement. We will monitor a number of quality measures to insure the three groups of patients are comparable.

6. Response: The sample size calculation is based on the primary outcome of proximal diminutive ADR. Additional observations will be used as hypothesis-generating for future studies.

7. Response: Permission will be sought from the IRB to contact the patients at 30 days by phone and if patients report that they have had complications including ER visit or hospital admission, follow up data will be obtained (with the patients' permission) from the computerized patient record or from the local admitting hospital. It is important to track the 30 day complications since patients have been admitted to local hospital because of post procedural pain not associated with perforation but possibly due to the large amount of air insufflated especially in those who had air insufflation colonoscopy.

8. v) **Sample size:** Response: Based on more preliminary data collected in a RCT supported by the ASGE on ADR with the combined chromoendoscopy and water method, we have recalculated the number of subjects required for the study.

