Examination under water may be difficult with poor preparation as the residual stool alters the color and turbidity of the water and in cases with chromoendoscopy combined with the water method, turning the water green instead of blue and impairing visibility. Our experience indicated that water exchange by intermittent suctioning of dirty water and infusion of clean water will improve the visualization of the colonic lumen. Which patient will have poor preparation, however, is unpredictable. To overcome this unavoidable problem, we have adopted this colonoscopist-controlled approach of water exchange to remove any residual stool to improve the endoscopic examination. Since quality colonoscopy is ultimately the responsibility and pride of the colonoscopist, a method that is under his/her direct control during colonoscopy is the focus of our investigation.

(f) Data collection methods, intervals, and follow-up procedures:

Follow up care after the procedure

The research coordinator will call the patients after the colonoscopy at 24 hours to conduct the post procedural evaluation including any complications and to document patient satisfaction and address any questions or concerns from the patients (routine care applicable to all research subjects). Patients are advised to contact the research team or local emergency department if they notice any post procedural discomfort or pain. Patient will be contacted by phone at 30 day to document any adverse events including post procedural complications that may lead to emergency department visits or hospitalization.

The colonoscopist will review the pathology report of all lesions biopsied or removed and will notify the patients by mail of the results and the future follow up plan. Patients are generally advised to follow up with their primary care provider unless they have a complication or a significant pathology i.e. malignant polyp that requires further management discussion and referral.

Prospective data gathering (Table 11).

Table 11: List of quality measures, their purposes, and when the data will be collected.			
Data to be monitored ^a (purpose)	Baseline	During Recover	Up to 30 days
Findings – polypoid and flat lesions (primary and secondary outcomes)	X		
Cecal intubation (secondary outcome)	X		
Total medications during colonoscopy (secondary outcome)	X		
Maximum pain score during colonoscopy (quality measure)	X	X	
Additional medications during colonoscopy (quality measure)	X		

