Risk from time spent in responding to questionnaires: All questionnaires will be kept as concise as possible to minimize the time required to complete them.

Risk from discomfort associated with colonoscopy: Experienced endoscopists will perform and trained personnel will assist in the performance of the colonoscopy.

In addition, the following measures will be implemented to minimize risks for the subjects:

1. Enrollment of subjects will adhere to the inclusion and exclusion criteria.

2. The subjects will be given instructions to notify the study personnel if they have any concerns or untoward symptoms. They will be given the name and phone number of the site investigator and coordinator. An alternative number to one of the research team members will be given to subjects if they are not available. If an adverse event associated with the study should occur, the patients can contact one of the research team members, who will arrange appropriate and timely evaluations.

3. Subjects will be informed of new findings that may affect their decision to remain in the study.

4. VA good clinical practice guidelines will be followed.

5. VA information security measure will be implemented: Written documents and records will be coded so that the identity of the patient is protected. When not in use by the research team, these documents, records and codes will be placed in a locked file cabinet. Key access is available to members of the research team only. All computerized data will be placed in password protected computers. Password access will be available to members of the research team. These procedures are likely effective in protecting confidentiality.

(3) Potential benefit of the Proposed Research to the Subject and Others.

There are no known benefits to the research subjects.

(4) Importance of the Knowledge to be gained.

The result of the study may reveal if the additional dye staining (chromoendoscopy) is more or less efficacious, or no difference compared with the water method or the conventional air method in terms of finding more lesions (polypoid or flat lesions - hyperplastic and adenomatous polyps or cancers).

Therapeutic alternatives: All subjects in the study method group can undergo colonoscopy using the conventional air method.

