The identity of the subjects will be coded so that the data sheet with patient information will be de-linked from the patient identification. The coded video recording does not contain any patient identifier. The code will be kept in separate locked location and password access-protected computer (shared drive on the VA computer). When not in use by member of the research team all hard copies of coded patient information will be locked in file cabinet in designated location with locked access (e.g. investigators' office). All patient data transferred to computerized spread sheets will be stored in computers protected by password. Password access will be available to members of the research team only. At designated time after completion of the study (e.g. after publication of results), all stored data will be destroyed or erased. These measures are taken to comply with HIPAA requirements. The site investigators will review any complications and bring the occurrence to the attention of the Institutional Review Board.

Description of how adverse events are graded:

The main interventions are conventional method versus study methods. A grading scale will be used to describe adverse events if the need arises: 1=mild, 2=moderate, 3=severe, 4=life-threatening, 5=fatal. The attribution scale is 1=definitely not related, 2=probably not related, 3=possibly related, 4=probably related, 5=definitely related to the study interventions.

Plan for adverse event reporting:

The site PI will review all adverse events.

The site PI will promptly report any serious adverse events or unanticipated problems involving risks to study subjects in accordance with regulations: reportable adverse effects arising from any research procedures will be submitted promptly to the IRB. Although they are not anticipated to occur, deaths will be reported within 24 hours to the IRB. Unanticipated problems or Serious Adverse Events in research subjects will be reported to the IRB within 5 working days of awareness of the event and written reports will be submitted to the IRB no later than 15 calendar days after the event.

All reportable adverse events will be compiled, and reported in summary form, on an annual basis to the IRB, and at the conclusion of the study.

Performance and frequency of safety reviews:

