The site investigators will perform safety reviews for all patients enrolled in this study on a weekly basis. The site PI of the study is responsible for carrying out continuous monitoring of accrual, data quality, and adverse events. The local study monitoring team will review the accumulating data regarding overall safety and efficacy of treatments employed in the trial. The study monitoring team will meet (twice a year) to review adverse events and subject safety issues.

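### Thirty-day complications depend on the patient reporting them, and the 15-day written IRB deadline, counted from the event, can pass before the team knows of it

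*Combined protocol and SAP*

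**What the plan says.** Section (4)(f), under follow-up care, schedules two contacts after the procedure, both by telephone. The first: "The research coordinator will call the patients after the colonoscopy at 24 hours to conduct the post procedural evaluation including any complications". The second: "Patient will be contacted by phone at 30 day to document any adverse events including post procedural complications".

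The Response to reviewers, Critique 2, item 7, says when records are consulted: "if patients report that they have had complications including ER visit or hospital admission, follow up data will be obtained". This is done with the patient's permission, "from the computerized patient record or from the local admitting hospital". The same item explains that tracking to 30 days matters because patients have been admitted to local hospitals with post-procedural pain.

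Two statements invite contact between the calls. Section (4)(f) says: "Patients are advised to contact the research team or local emergency department if they notice any post procedural discomfort or pain". Human Subjects (2)(b) says: "The subjects will be given instructions to notify the study personnel if they have any concerns or untoward symptoms". Human Subjects (5) adds: "The site investigators will perform safety reviews for all patients enrolled in this study on a weekly basis".

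The adverse event reporting plan in Human Subjects (5) has three IRB limits. Serious adverse events and unanticipated problems are reported within 5 working days of awareness. For the written report, "written reports will be submitted to the IRB no later than 15 calendar days after the event". Deaths are reported within 24 hours, with no stated start.

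Table 10 lists complications up to 30 days as a secondary outcome, including perforation, bleeding and severe abdominal pain leading to an emergency visit or admission.

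**The concern.** Every stated route by which a delayed complication enters the data starts with the patient speaking to the team. A patient who has died, is still in hospital or does not answer at day 30 starts none of them, and no section says what happens next. The rule is weakest for the most serious outcomes. What is at stake is the completeness of the trial's only delayed-harm outcome.

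The reporting plan has a related weakness. It starts one clock when the team learns of the event and another when the event occurs. With up to 29 days between scheduled calls, the second clock can run out before the first has started.

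**Working it through.** The documents state no figure to reproduce here. The check is a comparison of passages followed by date arithmetic.

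**Does any other passage close the ascertainment gap?**

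- *Patient-initiated contact* (section (4)(f); Human Subjects (2)(b)): it still depends on the patient. Section (4)(f) also offers the local emergency department as an alternative to the research team, so a patient can follow the advice without the team hearing of it.
- *Weekly safety review and continuous monitoring by the principal investigator* (Human Subjects (5)): no data source is named. Nothing says that records are searched.
- *Review of existing medical records* (Human Subjects (1)(b)): the study does use the computerized record, but the examples given are baseline items such as age, sex, illnesses and medications.
- *Dropout rule* (section (4)(g), differential dropout): it counts unexamined segments as having no adenomas. It does not cover missing complication data.

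The gap is narrowed but not closed.

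**When does the written deadline pass before awareness?**

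Inputs: colonoscopy on day 0; event on day d; written report due on day d + 15; event first learned of at the call on day 30. The deadline has already passed if d + 15 < 30, that is, if d < 15.

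| Event day d | Written report due (d + 15) | Position at the day-30 call |
|---|---|---|
| 2 | 17 | 13 days overdue |
| 10 | 25 | 5 days overdue |
| 14 | 29 | 1 day overdue |
| 15 | 30 | due that day |
| 20 | 35 | 5 days left |

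The interval after the 24-hour call is days 2 to 30, which is 29 days. Days 2 to 14 are affected: 13 of 29, or 45%. This is a share of calendar days, not of events, and it applies only to events first learned of at the day-30 call.

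The first report, 5 working days after awareness on day 30, falls due about day 37 (30 + 7 calendar days). For an event on day 10, the written report would be due on day 25, about 12 days before the first report.

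**How many events or patients?**

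The documents give no delayed-complication rate and no non-contact rate. The ranges below are assumptions that show scale only.

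- Delayed-complication rate of 0.1% to 1.0%: 330 × 0.001 = 0.33 to 330 × 0.01 = 3.3 events in all, or 0.11 to 1.1 per arm of 110. These are events occurring, not events missed.
- Non-contact of 5% to 10% at day 30: 330 × 0.05 = 16.5 to 330 × 0.10 = 33 patients with no completed call.

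**The case against.** The strongest reply is that the plan is not silent between the calls. Patients are told to make contact, investigators review safety weekly, and the principal investigator monitors adverse events continuously. That stands against a reading that complications are learned of only at day 30, or that the worst ones are certain to be missed. The documents support only that they can be missed.

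Other stronger readings are tempting and not supported:

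- A reader might apply the 1.1% in Human Subjects (1)(a) to 330 patients and expect about 3.6 events in the gap. That figure is for hypotension, hypoxia and arrhythmia with sedated colonoscopy, which are monitored around the procedure. It is not a delayed-complication rate.
- A reader might infer that losses differ by arm, because Critique 2, item 7, links pain admissions especially to air insufflation. That concerns how often events occur, not how often they go unrecorded. The same calls apply to all arms, and patients are blinded.
- A reader might infer that permission for records is sought only once a complication is reported. The text gives no timing, and the consent pages are not available for this review.
- A reader might say that the IRB rule cannot be met for half of the follow-up window. The 5-working-day limit can always be met, because it starts at awareness. The written limit fails only for an event before day 15 that no other route has brought to light. For events on days 15 to 21 it falls due before the first report, but it can still be met.

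It is also fair to say that the primary outcome is untouched and that the status of complications is mixed. Table 10 makes them a secondary outcome, Table 11 calls them co-variables, and the list in Specific Aims (b) omits them. This limits the weight of the point but does not remove it, because Critique 2, item 7, itself calls 30-day tracking important.

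**Conclusion.** The point holds in limited form and is worth acting on. The stated procedure has no route into the data for a patient who cannot speak for themselves at day 30, so the 30-day complication outcome can be incomplete for the most serious events. The size cannot be derived from the documents. With counts as low as those assumed above, losing one event could change what an arm shows, but no bias between arms is demonstrated.

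The conflict between the reporting clocks is exact. It follows from the text alone, given an event before day 15 that first becomes known at the day-30 call. The conclusion assumes that the weekly review has no independent record source, since none is named. If it does search records, stating so would answer much of the first part.

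**What to change.** 1. In Critique 2, item 7, and section (4)(f), state that the computerized patient record of every randomised patient is checked at day 30, whether or not the call succeeds and whether or not the patient reports anything, using the same procedure in all three arms. Use the weekly review in Human Subjects (5) to cover patients still within their 30 days, and name the record as its source. Make sure that permission to obtain outside-hospital records is in place at consent, because the VA record may not show local admissions. If the consent form already gives it, nothing needs to be added there.
2. In the adverse event reporting plan, reconcile the starting points of the 5-working-day, 15-day and 24-hour clocks with each other and with the applicable IRB rules, so that a written deadline cannot expire before the team is aware of the event.

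The cost is a short record look-up for 330 patients by the existing coordinator, a few sentences of text and, if needed, one consent sentence. A few more complications may be counted. Treatment, sample size and primary analysis do not change.
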